## **5.2 Schedule for remote (previous) cases**

Cases of previous myocarditis and pericarditis will be identified from chart review using the same criteria as new cases. For example, if a patient case is out of the immediate post-diagnosis window or their experience of myocarditis/pericarditis occurrence more than 12 months ago, we will extract relevant information for Brighton diagnostic criteria from chart review. We will review relevant investigations that have already been completed previously rather than repeat delayed testing. These patients will be approached to participate in the surveillance study as outlined previously.

After consent, they will join the study schedule at the nearest scheduled study visit e.g. If diagnosis was 13 months ago, they will join the 12-month visit. Each visit will have a range e.g., 12-month visit range will be 12-15 months. This will allow for health outcomes to be retrieved retrospectively and also collected moving forward from the time of joining the study.

## **6. DATA MANAGEMENT, STATISTICAL ANALYSIS, KNOWLEDGE TRANSLATION**

### **6.1 Data collection**

A single electronic case report form will be used. Data will be collected and managed using REDCap (Research Electronic Data Capture) electronic data capture tools, including electronic case report form (eCRF) (<https://www.project-redcap.org/>). REDCap is a secure, web-based application designed to support data capture, providing 1) an intuitive interface for validated data entry; 2) audit trails for tracking data manipulation and export procedures; 3) automated export procedures for seamless data downloads to common statistical packages; and 4) procedures for importing data from external sources. REDCap is the most widely used data solution in the world, compliant with all security and privacy measures in Canada.

### **6.2 Sample size estimation**

We aim to enroll as many patients as possible. For our sample size calculation, we will use international comparison cohorts including from Israel as well as Canadian PHAC adverse events following immunization (AEFI) reports. For example, PHAC has 1,061 cases of myocarditis/pericarditis that meet Brighton Criteria levels 1 to 3. Mevorach et al. (2021) in Israel had 283 cases in 5.1 million fully vaccinated subjects (Pfizer only). If we scale this to Canada with a population of approximately 38 million people, the estimate is 2,094 cases in Canada (Mevorach et al., 2021). A second study from Israel reported 54 cases in 2.5 million vaccinated subjects (Pfizer only). If we also scale this to 38 million people in Canada, the estimate is 810 cases (Witberg et al., 2021). This provides us with a range of 810 to 2,094 cases. If we use a lower limit of capturing 60% of the 810 cases, accounting for loss to follow-up, our lower limit will be 486 cases. Our sample size will be between the lower and upper limits, and our goal will be to identify all 1,061 cases reported to PHAC as a starting point, while adding cases from our collaborators.

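### Section 6.2 scales rates per vaccinated person to the whole Canadian population and sets its floor on fewer cases than the 1,061 already reported, so the stated range of 486 to 2,094 is not supported by its own inputs

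*Protocol*

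**What the plan says.** Section 6.2 opens with the aim of enrolling as many patients as can be found and then builds a range from outside counts.

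- The first Israeli source had "283 cases in 5.1 million fully vaccinated subjects (Pfizer only"). The protocol continues: "If we scale this to Canada with a population of approximately 38 million people, the estimate is 2,094 cases in Canada".
- The second had "54 cases in 2.5 million vaccinated subjects (Pfizer only"). The protocol continues: "If we also scale this to 38 million people in Canada, the estimate is 810 cases".
- The two results are joined: "This provides us with a range of 810 to 2,094 cases".
- The floor follows by taking "a lower limit of capturing 60% of the 810 cases, accounting for loss to follow-up, our lower limit will be 486 cases".
- The conclusion is "Our sample size will be between the lower and upper limits", with all the cases known to the Public Health Agency of Canada (PHAC) as the starting goal.

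The same paragraph also gives a Canadian count: "PHAC has 1,061 cases of myocarditis/pericarditis that meet Brighton Criteria levels 1 to 3". Section 4.4 makes levels 1 to 3 the levels the study includes, and Section 4.6 excludes levels 4 and 5.

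**The concern.** Three things in the construction do not fit together.

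1. Both source rates have vaccinated people in the denominator, but the multiplier is every resident. No vaccine coverage is stated or applied.
2. The low case count of 810 is below the number of Canadian reports that the same paragraph says already meet the study's inclusion levels.
3. The figure of 2,094 is an estimate of cases occurring in Canada, yet it serves as the upper limit on cases in the study. The factor for capture and loss appears at the lower end only.

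Apart from the goal of finding the 1,061 reported cases, this range is the only size the protocol gives. Section 3.2 plans a risk score for major adverse cardiovascular events and a comparison of treated with untreated patients. Whether either is feasible depends on how many patients, and so how many events, the study can expect.

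**Working it through.** **Inputs.** From Section 6.2: 283 cases per 5.1 million fully vaccinated; 54 cases per 2.5 million vaccinated; population about 38 million; 60% as the lowest capture; 1,061 PHAC reports. Vaccine coverage in Canada is not in the protocol, so 70% to 90% is assumed here.

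**Step 1. Reproduce the stated figures.** Cases = (source cases / source vaccinated) × 38 million.

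- 283 / 5.1 × 38 = 2,108.6, against 2,094 stated (0.7% apart).
- 54 / 2.5 × 38 = 820.8, against 810 stated (1.3% apart).
- 0.60 × 810 = 486, exact.

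The small gaps fit a shortened scale factor: 38 / 5.1 = 7.45 and 283 × 7.4 = 2,094; 38 / 2.5 = 15.2 and 54 × 15 = 810. The whole population was therefore the multiplier, with no reduction for coverage.

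**Step 2. Use vaccinated people as the multiplier.** Cases = rate × 38 million × coverage.

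| Assumed coverage | Lower source | Upper source |
|---|---|---|
| 100% (implicit in the protocol) | 821 | 2,109 |
| 90% | 739 | 1,898 |
| 80% | 657 | 1,687 |
| 70% | 575 | 1,476 |

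Each 10 points of coverage below 100% takes about 82 cases off the lower estimate and 211 off the upper.

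**Step 3. Compare the floor with the Canadian count.**

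- 810 / 1,061 = 0.76, so the low estimate is 24% below the reports already in hand.
- 486 / 1,061 = 0.46, so the floor is less than half of them.
- The protocol's own 60% applied to the reports: 0.60 × 1,061 = 636.6, about 637.

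Correcting coverage alone would move the lower source further from the Canadian count (575 to 739 against 1,061). That source is therefore a poor base for the floor, however the denominator is handled.

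**Step 4. Read the upper limit.** As cases enrolled, 2,094 requires 2,094 cases × 100% capture × 100% retention. Neither percentage is stated.

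**Step 5. What it does to precision.** With an illustrative event rate of 10% (assumed, not from the protocol), the 95% half-width is 1.96 × √(0.1 × 0.9 / n):

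| n | Expected events | Half-width |
|---|---|---|
| 486 | 49 | ±2.7 points |
| 637 | 64 | ±2.3 points |
| 2,094 | 209 | ±1.3 points |

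Moving the floor from 486 to 637 changes the half-width by about 0.3 points (2.67 to 2.33).

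**The case against.** The strongest reply is that this is a rough feasibility count in a study that takes every patient it can find. No alpha, power or precision statement depends on it. That is right, and it limits how much weight the point carries.

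**Direction.** Several simplifications may pull against the coverage error. Both sources are Pfizer only, while Section 2.7 reports a markedly higher risk with Pfizer followed by Moderna. Both are titled as myocarditis studies in the reference list, whereas the cohort includes pericarditis. Boosters continue (Section 2.3) and the cohort end date is open (Section 4.8). COVID-19 and MIS-C/A cases (Section 4.3) are not in the scaling at all. This stands: it cannot be said that the study will be smaller than stated, only that the stated method does not yield the stated counts.

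**The 60%.** The text words it as the lowest capture, so pairing it with the low count and leaving the high count whole can be read as a worst-to-best bracket. That reading is fair. A reader might infer that 2,094 is unattainable under the plan's own assumption, but 60% is a floor on capture and not a fixed rate. What remains is that full capture and no loss at the top end are left unsaid.

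**The 1,061.** A reader might call these confirmed cases that flatly contradict 810. They are reports at levels 1 to 3, which include probable and possible cases, and the study has yet to identify and enrol them. They also cover both conditions and are not restricted to Pfizer, so a scaled Pfizer-only count that may cover myocarditis alone can lie below them. This explains the gap but does not make 810 a good floor when a Canadian count at the study's own inclusion levels stands beside it.

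**The printed totals.** Solving backwards, 810 implies 37.5 million people and 2,094 implies 37.7 million. A reader might infer that two populations were used. Step 1 shows that this is rounding, and it is not a finding.

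**Conclusion.** The point holds, with modest impact. Section 6.2 applies rates per vaccinated person to all residents, which is valid only at 100% vaccination. For the method stated, 810 and 2,094 are too high; at an assumed 70% to 90% coverage they would be about 575 to 739 and 1,476 to 1,898. The size of this error cannot be fixed from the protocol, and the net direction after the other simplifications is unknown.

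The floor of 486 rests on a case count 24% below the reports that the same paragraph places at the study's inclusion levels. At the plan's own worst-case capture, those reports give about 637. The upper limit carries unstated assumptions of full capture and no loss.

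It is tempting to apply 60% at both ends and quote 637 to 1,256 (0.60 × 2,094 = 1,256). That should not be adopted: 1,256 still carries the coverage error, and it treats the lowest capture as the expected one.

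**What to change.** Restate Section 6.2:

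- **Lower limit.** Use the 1,061 reported cases as the base, with the date of the count. At 60% capture this gives about 637.
- **Upper limit.** Either multiply the rate by the number vaccinated in Canada, with date and source and with the same definition of vaccinated as the rate's denominator, or drop the Israeli scaling.
- **Capture and retention.** State them as two separate quantities, and give the values assumed at the upper end as well as the lower.
- **Scope.** Say that the range covers vaccine-associated cases only, or add figures for the COVID-19 and MIS-C/A groups.

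The cost is rewording, and an upper size that may be less favourable. No extra patients or procedures are needed.

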### **6.3 Statistical analysis**

The study will have a comprehensive Statistical Analysis Plan authored by the study statistician and agreed by the Investigators before the final analysis. The Centre for Cardiovascular Innovation will manage and analyze study data.

#### 6.4 Gender-based Analysis Plus

Analyses to date suggest that age and gender impact the risk of myocarditis and/or pericarditis following mRNA COVID-19 vaccination. Young men are more predisposed to myocarditis than other groups (e.g., Farahmand et al., 2020). To learn more about how myocarditis and/or pericarditis may impact different groups of people following mRNA COVID-19 vaccination, we plan to collect data about the patients' sex and age, as well as culture, race, ethnicity, occupation, ability, socioeconomics, and gender. We will strive to include patient representatives from diverse backgrounds in our stakeholder consultations and on our Steering Committee to understand their priorities and to refine our data collection, knowledge translation and dissemination strategies based on their experiences and needs. This will ensure sex, gender, and other intersecting identify factors, are integrated throughout the project lifecycle, and the Gender-based Analysis Plus framework is used to inform future vaccination programs.

#### 6.5 Knowledge translation plan

Effective knowledge translation (KT) is foundational to this project. The Canadian Cardiovascular Society will use evidence-based models to develop a KT plan and resources to raise awareness and drive uptake over the duration of the funding period and beyond. To optimize collaboration and uptake, strategic activities and KT tools will be individualized for target stakeholder and community groups. The Canadian Cardiovascular Society will:

- Update KT tools (clinical considerations and non-traditional (social approach to Management) with latest evidence; individualize for audience needs: cardiologists and other healthcare professionals as appropriate.
- Disseminate KT tools in print and electronically to the Canadian Cardiovascular Society membership, national, provincial and territorial associations (as well as national, provincial and regional First Nations, Indigenous and Metis health organizations).
- Develop & launch companion patient tools regarding myocarditis/pericarditis following mRNA vaccine.
- Develop and host a series of webinars to raise awareness of the surveillance study, provide overviews of KT tools with tips for use in practice and provide live forums for discussion plus Q&A.

We will canvass decision-makers for communication preferences and tailor knowledge translation materials, such as webinars, social media strategies, policy briefs and infographics and presentations accordingly. Materials will be translated in English, French and possibly other languages. The Canadian Cardiovascular Society will engage with the Public Health Agency of Canada and provincial and territorial public health agencies over the course of the project. The connections established with provincial and national health partners will also support the availability of timely evidence from this project for decision-makers across the country.

A communications plan will support the above initiatives and include the best approach to informing all stakeholders with the right information, through the right channels at the right time. Channels of communication may include journal ads, the Canadian Cardiovascular Society membership news, Project e-newsletters, social media, web content. Key project information will be housed on the Canadian Cardiovascular Society website over the funding period and beyond and will be reviewed and updated as new evidence becomes available.

[figure not shown]

## 7. APPENDICES

## 7.1 Appendix 1. Brighton Collaboration myocarditis case definition and levels of diagnostic certainty

Level of certainty 1 (definitive case)	
Histopathologic examination of myocardial tissue (autopsy or endomyocardial biopsy) showed myocardial inflammation	
OR	
Elevated myocardial biomarkers (at least one of the findings below)	
	Troponin T
	Troponin I
AND	
Abnormal imaging study	
	Abnormal cardiac magnetic resonance study (at least one of the findings below)
	Edema on T2-weighted study, typically patchy in nature
	Late gadolinium enhancement on T1-weighted study with an increased enhancement ratio between myocardial and skeletal muscle typically involving at least one non-ischemic regional distribution with recovery (myocyte injury).
OR	
	Abnormal echocardiogram (at least one of the findings below)
	New focal or diffuse left or right ventricular function abnormalities (e.g., decreased ejection fraction)
	Segmental wall motion abnormalities
	Global systolic or diastolic function depression or abnormality
	Ventricular dilation
	Wall thickness change
Level of certainty 2 (probable case)	
Clinical symptoms	
	Cardiac symptoms (at least one finding below)
	Acute chest pain or pressure
	Palpitations
	Dyspnea after exercise, at rest, or lying down
	Diaphoresis
	Sudden death
OR	
	Non-specific symptoms (at least two findings below)
	Fatigue
	Abdominal pain
	Dizziness or syncope
	Edema
	Cough
OR	
	Infants and young children (at least two findings below)
	Irritability
	Vomiting
	Poor feeding
	Tachypnea
	Lethargy
AND	
Testing supporting diagnosis (biomarkers, echocardiogram, and electrocardiogram)	
	Abnormal cardiac magnetic resonance study (see level 1 case definition)
OR	
	Elevated myocardial biomarkers (at least one of the findings below)
	Troponin T
	Troponin I
	Creatine kinase-myocardial band
OR	
	Abnormal echocardiogram (See level 1 case definition)
OR	
	Electrocardiogram abnormalities that are new and/or normalize on recovery (at least 1 of the findings below)
	Paroxysmal or sustained atrial or ventricular arrhythmias (premature atrial or ventricular beats, and/or supraventricular or ventricular tachycardia, interventricular conduction delay, abnormal Q waves, low voltages)
	AV nodal conduction delays or intraventricular conduction defects (atrioventricular block (grade I-III), new bundle branch block)
	Continuous ambulatory electrocardiographic monitoring that detects frequent atrial or ventricular ectopy
AND	
	No alternative diagnosis for symptoms
Level of certainty 3 (possible case)	
Clinical symptoms (see level 2 case definition)	
AND	
Testing supporting diagnosis (biomarkers and electrocardiogram)	
	Elevated biomarkers supporting evidence of inflammation (at least 1 of the findings below)
	Elevated c-reactive protein or high-sensitivity c-reactive protein
	Elevated erythrocyte sedimentation rate
	Elevated D-dimer
OR	
	Electrocardiogram abnormalities that are new and/or normalize on recovery (at least 1 of the findings below)
	ST-segment or T-wave abnormalities (elevation or inversion)
	Newly reduced r-wave height, low voltage, or abnormal q waves
	PACs and PVCs
AND	
	No alternative diagnosis for symptoms

7.2 Appendix 2. Brighton Collaboration myocarditis case definition flow chart

**Echocardiogram abnormalities:**

- New focal or diffuse left or right ventricular function abnormalities (e.g., decreased ejection fraction)
- Segmental wall motion abnormalities
- Global systolic or diastolic function depression/abnormality
- Ventricular dilation
- Wall thickness change

**cMR abnormalities:**

- Edema on T2 weighted study, typically patchy
- Late gadolinium enhancement on T1 weighted images with an increased enhancement ratio between myocardial and skeletal muscle typically involving ≥1 non-ischemic regional distribution with recovery (myocyte injury)

**Non-specific symptoms:**

- Fatigue
- Abdominal pain
- Dizziness or syncope
- Edema
- Cough

**Cardiac symptoms:**

- Acute chest pain or pressure
- Palpitations
- Dyspnea after exercise, at rest, or lying down
- Diaphoresis
- Sudden death

**Electrocardiogram abnormalities:**

- Paroxysmal or sustained atrial or ventricular arrhythmias (premature atrial or ventricular beats, and/or supraventricular or ventricular tachycardia, interventricular conduction delay, abnormal Q waves, low voltages)
- AV nodal conduction delays or intraventricular conduction defects (atrioventricular block (grade I-III), new bundle branch block)
- Continuous ambulatory electrocardiographic monitor that detects frequent atrial or ventricular ectopy

**Infant/child non-specific symptoms:**

- Irritability
- Vomiting
- Poor feeding
- Tachypnea
- Lethargy

[figure not shown]
**Non-specific Electrocardiogram abnormalities:**

- ST-segment of T-wave abnormalities (elevation of inversion)
- Premature atrial and ventricle contraction
- Newly reduced r-wave height, low voltage or abnormal q waves

**7.3 Appendix 3. Brighton Collaboration pericarditis case definition and levels of diagnostic certainty**

Level of certainty 1 (definitive case)	
	Histopathologic examination of myocardial tissue (autopsy or pericardial biopsy) showed pericardial inflammation OR Abnormal testing (at least two of the following three findings below): Evidence of abnormal fluid collection or pericardial inflammation by imaging (echocardiogram, magnetic resonance, cardiac magnetic resonance, computed tomography) OR Electrocardiogram abnormalities that are new or normalize on recovery (must have all findings below) Diffuse concave-upward ST-segment elevation ST-segment depression in augmented vector right PR-depression throughout the leads without reciprocal ST-segment changes OR Physical examination finding (at least one finding below) Pericardial friction rub Distant heart sounds (infants and children) Pulsus paradoxus
Level of certainty 2 (probable case)	
Clinical symptoms	Cardiac symptoms (at least one finding below) Acute chest pain or pressure Palpitations Dyspnea after exercise, at rest, or lying down Diaphoresis Sudden death OR Infants and young children (at least two findings below) Irritability Vomiting Poor feeding Tachypnea Lethargy AND Physical examination findings: (at least one finding below) Pericardial friction rub Pulsus paradoxus OR Evidence of abnormal fluid collection or pericardial inflammation by imaging (echocardiogram, magnetic resonance, cardiac magnetic resonance, computed tomography) OR Electrocardiogram abnormalities that are new and/or normalize on recovery (at least 1 finding below) Diffuse concave-upward ST-segment elevation ST-segment depression in augmented vector right PR-depression throughout the leads without reciprocal ST-segment changes AND No alternative diagnosis for symptoms (myocardial infarction, pulmonary embolus, mediastinitis etc.)
Level of certainty 3 (possible case)	
Clinical symptoms	Cardiac symptoms (at least one finding below) Acute chest pain or pressure Palpitations Dyspnea after exercise, at rest, or lying down AND Non-specific symptoms (at least two findings below) Cough Weakness Gastrointestinal – nausea, vomiting, diarrhea Shoulder/upper back pain Cyanosis Low grade intermittent fever Altered mental status Edema Fatigue OR Infants and young children (at least two findings below) Irritability Vomiting Poor feeding Tachypnea Lethargy AND Abnormal testing supporting diagnosis Abnormal chest radiograph showing enlarged heart OR Nonspecific electrocardiogram abnormalities other than those listed in LOC 1 and LOC 2 that are new or normalize on recovery AND No alternative diagnosis for symptoms (myocardial infarction, pulmonary embolus, mediastinitis etc.)

7.4 Appendix 4. Brighton Collaboration pericarditis case definition flow chart

[figure not shown]
**7.5 Appendix 5. Clinical symptoms associated with myocarditis and/or pericarditis.**

	Myocarditis	Pericarditis
Cardiac symptoms		
Acute chest pain or pressure, positional changes	X	X
Palpitations	X	X
Dyspnea after exercise, at rest, or lying down	X	X
Diaphoresis	X	X
Sudden death	X	X
Non-specific symptoms		
Fatigue, malaise	X	X
Abdominal pain	X	
Dizziness or syncope	X	
Edema	X	X
Cough	X	X
Cyanosis		X
Weakness		X
Altered mental status		X
Shoulder and/or upper back pain		X
Gastrointestinal – nausea +/- vomiting +/- diarrhea		X
Low grade intermittent fever ( $\geq 38^{\circ}$ Centigrade)		X
Infants and young children		
Irritability	X	X
Vomiting	X	X
Poor feeding	X	X
Lethargy	X	X
Tachypnea	X	X

7.6 Appendix 6. Multisystem Inflammatory Syndrome in Children and Adults (MIS-C/A) criteria

T.P. Vogel, K.A. Top, C. Karatzios et al.

Vaccine 39 (2021) 3037–3049

**Fig. 3.** Algorithm for utilization of the case definition for MIS-C/A. Note: Minimal to mild respiratory symptoms may be present and does not exclude a case of MIS-C/A, however a case must be excluded if there is concern for COVID-19-related pulmonary disease. One of the critical components of the case definition is that it is only applied when there is no clear alternative diagnosis for the reported event. Footnotes: a MIS-C=multisystem inflammatory syndrome in children, MIS-A=multisystem inflammatory syndrome in adults, CRP=C reactive protein (detected by any measure), ESR=erythrocyte sedimentation rate, BNP=brain natriuretic protein, NT-proBNP=N terminal pro-BNP, EKG=electrocardiogram, SARS-CoV-2=severe acute respiratory syndrome coronavirus-2, COVID-19=coronavirus disease 2019. b rash, erythema or cracking of the lips/mouth/pharynx, bilateral nonexudative conjunctivitis, erythema or edema of the hands or feet. c abdominal pain, vomiting, diarrhea. d altered mental status, headache, weakness, paresthesias, lethargy. e laboratory values are defined as low or high based on local laboratory norms. f echocardiographic signs: dysfunction, wall motion abnormality, coronary abnormality (dilation, aneurysm, echobrightness, lack of distal tapering), valvular regurgitation, pericardial effusion, evidence of abnormal left ventricular strain. g physical stigmata of heart failure: gallop (if diagnosed by expert) or rales, lower extremity edema, jugular venous distension, hepatosplenomegaly. h EKG changes consistent with myocarditis or myo-pericarditis: abnormal ST segments and/or arrhythmia and/or pathologic Q waves and/or AV conduction delay and/or PR segment depression and/or low voltage QRS. i laboratory evidence of SARS-CoV-2 infection: serologic evidence of SARS-CoV-2 infection OR SARS-CoV-2 antigen positivity OR SARS-CoV-2 nucleic acid amplification positivity. j if a known or suspected COVID-19 infection has not occurred within the preceding 12 weeks.

